### **DATA MONITORING**

The principal investigator will be responsible to ensure the study is conducted in accordance with the protocol, Declaration of Helsinki, and that the data recorded is valid. To achieve this objective the study will be continuously monitored and reviewed by the study team.

Clinical site monitoring is conducted to ensure that the rights and well-being of human subjects are protected, that the reported trial data are accurate, complete, and verifiable, and that the conduct of the trial is in compliance with the currently approved protocol/amendment(s) with the Good Clinical Practice (GCP).

## **DATA HANDLING AND RECORD KEEPING**

The collection of personal patient information will be limited to the amount necessary to achieve the aims of the research, so that no unneeded sensitive information is being collected. Only study personnel will collect data. Collected data will be de-identified and to be used for statistical analysis.

## **INSTITUTIONAL REVIEW BOARD**

The protocol, informed consent form(s), and all participant materials will be submitted to the Ethics Committee for review and approval. Approval of both the protocol and consent form must be obtained before any participant is enrolled. Any amendment to the protocol will require review and approval before the changes are implemented to the study.

## **CONSENT PROCESS**

Subjects will be approached when they come through the hospital for treatment and considered for elective CABG surgery. Each potential subject must provide written informed consent with full knowledge of the procedures involved. The informed consent must be fully explained by the investigator or member of the study staff including the study aims, methods, benefits and risks, and signed by the subject before enrollment into the study. Potential subjects will be informed that study participation is voluntary and that they may withdraw at any time. The subjects will be told that choosing against participation will not affect the care received for treatment. The subjects will be informed that they will be authorizing access of investigational staff to confidential medical records. The subjects will be given sufficient time to read the consent and ask any questions. Once the informed consent is signed, the subject will be given a copy of the document.

## **CONFLICT OF INTEREST**

No conflicts of interest have been reported

**APPENDIX II: CASE REPORT FORM (CRF)**

**CASE REPORT FORM (CRF)**  
**MYOCARDIAL PROTECTING ROLE OF GLUTAMINE IN PATIENTS WITH LOW**  
**EJECTION FRACTION UNDERGOING ELECTIVE ON-PUMP CORONARY**  
**ARTERY BYPASS GRAFT SURGERY**

Respondent code : .....

Name : .....

Medical record no.: .....

Attending doctor : .....

Date of birth / age : ...../...../..... years old

Sex : Male/ female (cross as not applicable)

Weight : ..... kg

Height : ..... cm

[figure not shown]
Address : .....  
.....

Telephone number : .....

Alternative number : .....

Diagnosis : .....

Note:

**Pre-Operative Laboratory Parameters**

Parameters	Value
Hb	
Hct	
Leukocyte	
Trombocyte	
SGOT	
SGPT	
Ur	
Cr	
Albumin	
pH	
pCO2	
pO2	
FiO2	
Na+	
K+	
HCO3-	
SatO2	
Lactate	
CRP	
HIV	
Hepatitis B	
Hepatitis C	

ECG:

CXR:

**Surgical Procedure, Aortic Cross-Clamp and CPB**

Parameters	Date	Time
No. of distal coronary artery graft		.....
Induction start	...../...../.....	.... : ....
Intervention administration		.... : ....
Bottle no. : _____	...../...../.....	
Incision	...../...../.....	.... : ....
Start of CPB	...../...../.....	.... : ....
Aortic cross-clamp start	...../...../.....	.... : ....
Aortic cross-clamp end	...../...../.....	.... : ....
End of CPB	...../...../.....	.... : ....
Skin closure suture	...../...../.....	.... : ....
Operating room departure	...../...../.....	.... : ....
ICU admission	...../...../.....	.... : ....
Extubation	...../...../.....	.... : ....
ICU discharge	...../...../.....	.... : ....

### Cardiac Index and Ejection Fraction Measurement

Parameters	Pre-operation	Time after CPB				
		5 minutes	30 minutes	2 hours	6 hours	24 hours
Cardiac Index	1: 2: 3:	1: 2: 3:	1: 2: 3:	1: 2: 3:	1: 2: 3:	1: 2: 3:
Ejection Fraction (EF)						
Echocardiography Operator	EF 1:  dr. _____  —  EF 2:  dr. _____  —					

### Right Atrial Appendage Tissue Examination

Parameters	Results
α-KG level	1: 2:
Myocardial injury score	1: 2:
Apoptotic index	1: 2:
Anti-cardiac troponin I expression	1: 2:

**Post-Operative Vasoactive and Inotropes**

Parameters	1	4	6	8	12	18	24	36	48
Dobutamine (mcg/kg/minute)									
Epinephrine (mcg/kg/minute)									
Milrinon (mcg/kg/minute)									
Vasopressin (unit/kg/minute)									
Norepinephrine (mcg/kg/minute)									
VIS*									

\*VIS = dopamine dose (in mcg/kg/minute) + dobutamine dose (in mcg/kg/minute) + 100 x epinephrine dose (in mcg/kg/minute) + 10 x milrinone doses (in mcg/kg/minute) + 10.000 x vasopressin dose (in unit/kg/minute) + 100 x norepinephrine dose (in mcg/kg/minute)

**Surgery Duration, Aortic Cross-Clamp Duration, ICU Care Duration and Ventilator Usage Duration**

Parameters	Results
Surgery duration (Incision – skin closure suture)	..... minutes
Aortic cross-clamp duration (Aortic cross clamp start – Aortic cross clamp end)	..... minutes
CPB duration (Start of CPB – End of CPB)	..... minutes
ICU care duration (ICU admission – ICU discharge)	..... hours
Ventilator usage duration (ICU admission – Extubation)	..... minutes

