### **Goals of the study:**

To analyze the effect of intravenous glutamine in low EF patients undergoing on-pump CABG surgery in:

1. Reducing myocardial damage by a decrease of myocardial injury score, apoptotic index and increase of anti-cardiac troponin I expression through right atrial appendage tissue sample, as well as decrease of troponin I level.
2. Improving myocardial metabolism by a decrease in plasma lactate levels, increase of plasma glutamine levels and alpha ketoglutarate ( $\alpha$ -KG) levels in the right atrial appendage tissue sample.
3. Improving hemodynamic profile through an increase in EF and cardiac index after CPB
4. Reducing postoperative morbidity by the decrease of ventilator duration, duration of intensive care, and use of postoperative vasoactive and inotropes

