Ejection fraction measurements are taken: (1) after induction and (2) at 5 minutes after CPB, through TEE examination using the modified Simpson method. Cardiac index (CI) measurements are taken: (1) after induction, (2) at 5 minutes, (3) at 2 hours, (4) at 6 hours, and (5) at 24 hours after CPB. The values are obtained from calculating cardiac output (CO) per body surface area (in m^2). Cardiac output is measured via a pulmonary artery catheter using thermodilution method. The measurements are performed three times, averaged, and considered valid if the variation between the three values is less than 10%. Body surface area is calculated using the Mosteller formula. Morbidity variables consist of ventilator time, postoperative use of vasoactive and inotropic agents, and duration of intensive care are collected from the medical record. Vasoactive and inotropic score (VIS) is calculated (VIS = dopamine dose [μg kg min] + dobutamine [μg kg min] + 100 × epinephrine dose [μg kg min] + 10,000 × vasopressin [units kg min] + 100 × norepinephrine dose [μg kg min]) using the maximum dosing rates of vasoactive and inotropic medications (μg kg min or IU kg min) during the first 24 hours after postoperative ICU admission.

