### **Reasons for Withdrawal or Termination:**

A subject may be discontinued from the study at any time if the subject or the investigator feels that it is not in the subject's best interest to continue. The following is a list of possible reasons the subjects will be **dropped out** from the study:

- Stroke after surgery
- Perioperative myocardial infarction based on type 5 myocardial infarct criteria
- Haemorrhage complications requiring repeat surgery
- Use of continuous veno-venous hemofiltration or haemodialysis after coronary artery bypass graft surgery
- Delayed sternal closure
- Aortic cross-clamp duration of > 120 minutes and/or cardiopulmonary bypass duration of >180 minutes

All subjects are free to withdraw from participation at any time, for any reason, specified or unspecified, and without prejudice. Reasonable attempts will be made by the investigator to provide a reason for subject withdrawals. The reason for the subject's withdrawal from the study will be specified in the subject's source documents and the Case Report Form (CRF). If a subject is withdrawn from treatment due to an adverse event, the subject will be followed and treated by the investigator until the adverse event has resolved or stabilized.

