#### Secondary Endpoint

Alpha-Ketoglutarate, myocardial injury score, apoptosis index, anti-cardiac troponin I expression, ejection fraction, cardiac index, plasma lactate, intensive care unit ventilation time, intensive care unit length of stay and vasoactive inotropic score.

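### Ventilator time and ICU stay each have a single end point and take no account of re-intubation, ICU readmission or death, so such patients may be scored as short or lost from the comparison.

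*Combined protocol and SAP*

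**What the plan says.** The Secondary Endpoint section of the SAP names "intensive care unit ventilation time, intensive care unit length of stay and vasoactive inotropic score" without defining them. Under Goals of the study, the fourth goal sets the direction of benefit: "Reducing postoperative morbidity by the decrease of ventilator duration, duration of intensive care, and use of postoperative vasoactive and inotropes". The Data Collection section adds only the source: "Morbidity variables consist of ventilator time, postoperative use of vasoactive and inotropic agents, and duration of intensive care are collected from the medical record".

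The operational definitions are in the Case Report Form (Appendix II). The durations table gives "Ventilator usage duration (ICU admission – Extubation"), in minutes, and "ICU care duration (ICU admission – ICU discharge"), in hours. Each end time comes from one row in the table of surgical and CPB times: one row for extubation and one for "ICU discharge". There is no row for a second extubation or for ICU readmission.

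The Research Sample Outcomes page separately records intubation (onset, duration, reason) and mortality (time, cause). No section links either entry to the two durations. The SAP has no rule for a missing end time and names no test for these endpoints.

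**The concern.** A duration is a sound morbidity measure only if a longer value always means a worse course. Two kinds of patient can break that ordering here.

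- **Failed extubation or ICU readmission.** If the interval closes at the earlier event, the second episode is not counted, and a complicated course is recorded as a short one.
- **Death in the ICU.** Someone who dies while ventilated has no extubation time, and someone who dies in the unit is not plainly discharged from it. Closing the interval at death gives a short value, which goal 4 reads as benefit. Leaving it blank removes the patient because the outcome was bad. Neither treatment places death below a long recovery.

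At stake is the direction of two morbidity comparisons. Deaths entered as short stays in the control arm would hide a real benefit of glutamine; in the glutamine arm they would create an apparent one. The Background says that in-hospital mortality in low-EF patients is up to four times that with normal EF, so such events are plausible, but it gives no absolute rate.

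**Working it through.** **Inputs from the documents.** The plan gives no expected value, SD or event rate for ventilator time, ICU stay, re-intubation or death, so it has no figure of its own to reproduce on this point. Only the arm size is used. The printed sample size does reproduce: 2 × [(1.96 + 0.84) × 0.04 / 0.032]² = 24.5, so 25 per group, and 50 + 10 = 60, or 30 per arm.

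**Reading the form**

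| Event | Recorded on the outcomes page | Enters the duration formula? |
|---|---|---|
| Later intubation | Onset, duration, reason | No link stated |
| ICU readmission | No field | No |
| Death | Time, cause | No link stated |

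**Uncounted ventilation, per patient.** The fall in an arm mean is the omitted hours divided by 30.
- 24 h: 24/30 = 0.8 h
- 48 h: 48/30 = 1.6 h
- 96 h: 96/30 = 3.2 h

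Example, if the earlier extubation is the one entered: extubated at 10 h, then ventilated for a further 48 h. The form shows 10 × 60 = 600 min; total ventilation is 58 × 60 = 3,480 min.

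**Death ranked shortest instead of longest, per patient.** The patient is compared with all 30 in the other arm, so the Mann-Whitney U moves by up to 30.
- Estimated probability that one arm does better: 30/(30 × 30) = 0.033, or 3.3 percentage points.
- SD of U under the null: √(30 × 30 × 61/12) = √4,575 = 67.6. The z shift is 30/67.6 = 0.44 for one death, 0.89 for two and 1.33 for three.

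**How many patients (assumed rates).** For an event rate of 2%, 5% or 10%, the expected number among 60 is 1.2, 3 or 6. The chance of at least one, 1 − (1 − p)⁶⁰, is 70%, 95% or 99.8%.

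**Effect on power (simulation, all inputs assumed).** Log-normal ICU stay, median 48 h, log-SD 0.5, true 30% shortening with glutamine, deaths entered at 12 h under the short rule, 30 per arm, Wilcoxon test, 3,000 to 4,000 trials per cell. Repeat runs differ by up to about 3 points.

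| Deaths (control / glutamine) | Closed at death (short) | Left missing | Worst rank |
|---|---|---|---|
| 0 / 0 | 76% | 76% | 76% |
| 1 / 0 | 64% | 75% | 80% |
| 2 / 0 | 52% | 74% | 84% |
| 3 / 0 | 37% | 73% | 88% |
| 1 / 1 | 72% | 74% | 70% |

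The rules separate widely only when deaths fall in one arm and are entered as short stays. With one death per arm they differ by about 4 points at most, close to simulation noise.

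**The case against.** The strongest reply is that the documents leave a gap and do not state a wrong rule. Four parts of it stand.

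- A reader might infer that ventilator time stops at the first extubation. The form says only extubation, and a site could enter the final one. The intubation entry on the outcomes page makes omission of a later episode likely, but that entry is not labelled as re-intubation.
- A reader might infer that an early death is scored as a short, favourable stay. Nothing says so; a blank is at least as natural. A patient who dies after leaving the ICU has a correct ICU duration.
- A reader might infer that these patients stay in the analysis because death is missing from the drop-out list, which opens with "The following is a list of possible reasons the subjects will be". That does not follow. The SAP defines no analysis population, and listed events such as stroke, type 5 infarction, re-operation for bleeding or dialysis may remove some of the same patients.
- The large losses of power depend on one-sided deaths and on the assumed 12 h value.

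It is also true that these are two of ten secondary endpoints, and that much of what is needed for a repair is already collected. What the reply does not answer is that the printed formulas, taken as they stand, never place an ICU death below a long recovery and provide no way to add a second episode. The choice is left to whoever completes the form.

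**Conclusion.** The point holds as a defect in how two secondary endpoints are defined. Each formula has one end point and ignores re-intubation, ICU readmission and death, so an affected patient may be scored as short or lost. The stronger statement, that the plan itself prescribes favourable scores for failed extubation and death, is not supported.

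The size cannot be computed from the documents. Per event, with 30 per arm, it is up to 3.3 percentage points on the rank-based probability for a death ranked shortest instead of longest, and 1.6 h on an arm mean for an uncounted 48 h episode. The consequence for power is material only if events are imbalanced between arms, and near nil with one death in each. The primary endpoints, plasma glutamine and troponin I, are not touched.

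**What to change.** Before unblinding, add a few lines to the SAP and the Case Report Form:

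1. Define ventilator time as total postoperative invasive ventilation, adding the intubation duration already recorded on the outcomes page, and label which extubation the time row refers to.
2. Define ICU stay to include readmission time where it is recorded.
3. Pre-specify one rule under which death before extubation or ICU discharge cannot count as favourable. Worst rank with a rank-based test is one option; ventilator-free and ICU-free time to a fixed day is another. Either is acceptable if fixed in advance.
4. Report deaths and re-intubations by arm beside the durations.

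The cost is small. ICU readmission may need one new field. The measure becomes a composite of duration and death, slightly less direct to interpret than mean hours. A rule chosen after unblinding could favour either arm, so the timing matters more than which option is taken.

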## Research Sample Outcomes

Criteria	Yes	No
Post CABG surgery stroke		
Perioperative MI (based on type 5 MI criteria)		
Hemorrhage complication requiring repeat surgery		
Require CVVH / HD after surgery		
Delayed sternal closure		
AoX >120 minutes / CPB time >180 minutes		
Mortality		
• Time: _____		
• Cause: _____		
Sepsis		
Post-operative arrhythmia		
• Onset		
• Arrhythmia type		
• Duration		
Acute renal failure		
Intubation		
• Onset		
• Duration		
• Reason		
Post-operative IABP usage		
• Onset		
• Duration		

Note:

**Research CRF Checklist**

Sample characteristics	
Preoperative laboratory parameters	
Surgical procedure, aortic cross-clamp and CPB	
Intervention liquid bottle number: _____	
Right atrial appendage tissue biopsy	

• a-KG level

• Myocardial injury score

• Apoptotic index

• Anti-cardiac troponin I expression

	
Plasma glutamine levels	
Troponin I levels	
Lactate levels	
Ejection Fraction	
Cardiac Index	
Post-operative vasoactive and inotropes	
Surgery duration, aortic cross-clamp duration, ICU care duration and ventilator usage duration	
Research sample outcomes	

Researcher: \_\_\_\_\_ Date: \_\_\_\_\_ Signature: \_\_\_\_\_
